The results from the main portion of the phase 2b study further indicate a potential benefit of treatment with jCell at the highest dose (6×10^6 hRPC), and especially in a subset of subjects who are defined by the ability to fixate centrally, with visual fields of at least 12 degrees, and with the study eye being at least equally functional to the non-study eye at study start (e.g., not significantly worse). In addition, preliminary data are also suggestive that the thickness of the remaining EZ layer as assessed by OCT at baseline may be a predictor of the subjects most likely to benefit from jCell treatment. The rationale for the proposed study is to answer a key safety question about jCell reinjection into a previously treated eye.

While retreatment of a patient in the fellow eye at least 12 months after the initial treatment has been shown to be safe to date, no subject has received a second injection in a previously treated eye. This is an important consideration, since data suggest that the effects of the injected cells are likely to decrease over time as the injected cells gradually disappear from the vitreous. Current estimates based on data to date suggest that an adequate dose is likely to be effective for at least 12 months (primary endpoint in the phase 2b study) and perhaps CONFIDENTIAL 14 of 37

longer in some subjects, but because the most important mechanism of action depends on the presence of the cells, which are not immortal, the effect will eventually diminish. Thus, it becomes important to establish the safety of retreatment.

In addition to safety, all subjects will be followed for efficacy for 12 months using the following methods: best corrected visual acuity (BCVA), mobility (maze), contrast sensitivity, and visual field testing.

Subjects may be asked to undergo additional testing to assess the characteristics of the jCell aggregate inside the eye (size and structure) and retinal sensitivity following treatment. Participation in these additional assessments at the jCyte low vision facility is optional and is not required for study participation.

2.0 **OBJECTIVES**

2.1 **Primary Objectives:**

The primary objective of the study is to assess the safety of repeat injection of jCell at a dose of 6×10^6 hRPC.

2.2 Secondary Objectives:

The secondary objectives of the study are to assess the impact of repeat injection of jCell on measures of visual function and functional vision over a 12 month period.

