3.0 STUDY DESIGN

This is a prospective, multi-center, single arm, Phase 2 study of human retinal progenitor cells (jCell) for the treatment of retinitis pigmentosa (RP). The study will include only subjects previously treated with jCell.

To assess reinjection of a previously treated eye, subjects who have previously been treated with jCell and desire a second treatment in the same eye will be enrolled. Subjects must have completed at least 12 months of follow up since the prior injection of jCell. Subjects who have had both eyes previously treated with jCell will only have one eye retreated; the eye to be retreated will preferably be the better seeing eye, but exceptions may be made by the study investigator, taking into consideration BCVA, prior response to treatment, and any other medical conditions that may indicate which eye is the best candidate for retreatment. Subjects will be followed for 12 months for safety and efficacy.

As noted above, subjects may be asked to undergo additional testing at the jCyte low vision facility to assess the characteristics of the jCell aggregate inside the eye (size and structure) and retinal sensitivity following treatment. These are exploratory assessments, and any/all may be discontinued if they are determined to be difficult to conduct or the results appear to be of little value in understanding the course of the injected cells and/or changes in retinal

sensitivity over time. Participation in these exploratory assessments is not required for study participation.

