13. SAFETY ANALYSES

The primary endpoint of this study is to obtain safety profiles for reinjection of jCell. The safety analyses of AEs and laboratory parameters will include descriptive statistics. Summaries of AEs will be generated by type (AE or SAE), body system and PT, severity, and relationship to study product.

All safety analyses will be based on the safety population.

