13.2 Adverse Events

All AE summaries will be restricted to treatment-emergent AEs (TEAEs), which are defined as those AEs that occurred after dosing and those existing AEs that worsened during the study. In the case of worsening in severity, a new entry is created in the database with start date equal to start of worsening. If it cannot be determined whether the AE is treatment-emergent due to a partial onset date, then it will be counted as such. Verbatim terms in the eCRFs will be mapped to SOCs and PTs using MedDRA, version 23.1.

AE summaries that are displayed by SOC and PTs will be ordered by descending subject count by SOC and PT within SOC. Summaries of the following types will be presented:

- Overall summary of TEAEs that contains a summary of the following:
 - Subject and event count of any TEAE
 - Subject and event count of TEAEs related to study drug
 - Subject and event count of serious TEAEs
 - Subject and event count of any serious TEAE related to study drug
 - Subject and event count of severe TEAEs related to study drug

Separate TEAE summary tables will be provided as follows:

- Subject incidence and event count of TEAEs by MedDRA SOC and PT.
- Subject incidence and event count of TEAEs by MedDRA SOC, PT, and highest severity. At each level of subject summarization, a subject is classified according to the highest severity if the subject reported more than one of the same event. Categories of severity will be "Mild", "Moderate", "Severe" and "Life threatening". Adverse events with missing severity will be assigned to "Severe" for this summary.
- Subject incidence and event count of TEAEs related to study drug by MedDRA SOC and PT. Related AEs are those reported as "Related" and "Possibly Related". At each level of subject summarization, a subject is classified according to the closest relationship if the subject reported more than one of the same event. Adverse events with a missing relationship will be considered related for this summary.
- Subject incidence and event count of serious TEAEs by MedDRA SOC and PT.

Separate listings of related TEAEs and SAEs will be provided.

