- All observed time values will be presented using a 24-hour clock HH:MM:SS format (e.g., 01:35:45 or 11:26). Seconds will only be reported if they were measured as part of the study.
- The last footnote will be "PROGRAM SOURCE:...\xx.sas, DATA CUTOFF DATE: DD Mmm YYYY, RUN DATE: DD Mmm YYYY hh:mm".

Missing or Incomplete Dates (i.e., Adverse Events and Concomitant Medications)

The most conservative approach will be systematically considered. If the adverse event (AE) onset date is missing/incomplete, it is assumed to have occurred during the study treatment phase (i.e., considered a treatment-emergent AE) except if the partial onset date or other data, such as the stop date, indicates differently. Similarly, a medication with partial start and stop dates could be considered as both a prior and concomitant medication.

The following algorithms will be applied to missing and incomplete start and stop dates:

Start Dates

- If the day portion of the start date is missing, then the start date will be estimated to be equal to the date of the first dose of study drug, provided the start month and year are the same as the date of the first dose of study drug and stop date is either after the date of the first dose of study drug or completely missing. Otherwise, the missing day portion will be estimated as "01."
- If both the day and month portions of the start date are missing, then the start date will be estimated to be equal to the date of the first dose of study drug, provided the start year is the same as the date of the first dose of study drug and stop date is either after the date of the first dose of study drug or completely missing. Otherwise, the event will be assumed to start on the first day of the given year (e.g. ??-???-2013 is estimated as 01-JAN-2013).
- If the start date is completely missing and stop date is either after the date of the study drug administration or completely missing, then the start date will be estimated to be equal to the date of study drug dosing. Otherwise, the start date will be estimated to be the first day of the same year as the stop date.

All other non-AE and non-concomitant medication day calculations where only partial dates are available will be handled as follows: the first day of the month will be used in the calculations if the day part of a start date is missing, and January 1 will be used if both the month and day parts of a start date are missing.

jCyte, Inc Protocol No. JC02-2

Stop Dates

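### In the text available, the TEAE tables do not separate the re-injected eye from the fellow eye, so ocular adverse event incidence is an either-eye figure

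*SAP*

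**What the plan says.** Protocol 1.3 gives the purpose as to "answer a key safety question about jCell reinjection into a previously treated eye". SAP 13 makes this primary: "The primary endpoint of this study is to obtain safety profiles for reinjection of jCell". Protocol 3.2.2 puts the incidence and severity of TEAEs first among the main safety criteria. Each subject has one eye injected in this study, but the fellow eye may have had jCell earlier. Protocol 3.0 says: "Subjects who have had both eyes previously treated with jCell will only have one eye retreated".

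SAP 13 and Protocol 9.3 name the dimensions of the adverse event summaries: type, body system and preferred term, severity, and relationship. Eye is not among them. The core table in SAP 13.2 is "Subject incidence and event count of TEAEs by MedDRA SOC and PT", and SAP section 6 says that adverse event percentages use subjects as the denominator. For the severity table, "a subject is classified according to the highest severity if the subject reported more than one of the same event". For the related-event table, "a subject is classified according to the closest relationship if the subject reported more than one of the same event". In Appendix B, Tables 14.3.2.1 to 14.3.2.5 carry no eye label.

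Other ocular outputs are by eye. Slit lamp, fundus, IOP, BCVA, visual field and contrast sensitivity each have separate study-eye and non-study-eye tables, and SAP 13.3.5 reports OCT for both eyes.

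**The concern.** Re-injection exposes one eye. A fellow-eye event is background, or at most a late effect of an earlier treatment. If SAP 13.2 is followed as written, a subject with an event only in the fellow eye is counted exactly like a subject with that event in the re-injected eye. No listed TEAE table would then give the incidence, severity or relationship of ocular events in the eye the study is about.

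The severity rule adds a second effect. When the same preferred term occurs in both eyes, the grade shown for the subject may be the fellow eye's grade. At 25 to 30 subjects, one misplaced subject is 4.0% (1/25) or 3.3% (1/30) of the denominator, enough to be visible in a row.

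**Working it through.** The plan states no event rate, and its 25-30 is an availability figure, so there is no plan figure to reproduce. The check is on direction first, then size.

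**Inputs.** n = 25 to 30 (SAP 5); one injected eye per subject (SAP 4); subjects as denominator (SAP 6); highest-severity rule (SAP 13.2). Ocular event rates by eye are not in the documents.

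**Direction.** Let p_s be the study-eye rate and p_f the fellow-eye rate for a preferred term. The table shows the rate in either eye, which lies between max(p_s, p_f) and min(1, p_s + p_f). It is never below p_s, and the excess is at most p_f. All combinations of study-eye and fellow-eye severity (none to life-threatening) were enumerated:

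- Subject incidence: either-eye never below study-eye.
- Event count: never below, even if a bilateral event is recorded once.
- Cumulative severity (a given grade or worse): never below.
- A single severity row: it can fall below the study-eye figure whenever the fellow eye has a higher grade.

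**Example of the exception.** Of 25 subjects, 5 have a mild study-eye event, and 2 of those 5 also have a severe fellow-eye event of the same preferred term.

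| Row of Table 14.3.2.3 | Study eye only | As planned |
|---|---|---|
| Mild | 5/25 (20%) | 3/25 (12%) |
| Severe | 0/25 | 2/25 (8%) |
| Any severity | 5/25 (20%) | 5/25 (20%) |

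**Size with no assumed rate.** Take one fellow-eye-only event in a row that is empty for the study eye. The Clopper-Pearson 95% upper limit for 0 events is 1 − 0.025^(1/n). For 1 event it is the p that solves (1 − p)^n + n·p·(1 − p)^(n−1) = 0.025.

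| n | 0 events | 1 event |
|---|---|---|
| 25 | 0%, upper limit 13.7% | 4.0%, upper limit 20.4% |
| 30 | 0%, upper limit 11.6% | 3.3%, upper limit 17.2% |

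The limits only gauge the shift; the plan itself is descriptive.

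**Size with assumed rates (illustration only).** Assume p_s = 20% and independent eyes. The either-eye rate is 1 − 0.80(1 − p_f). The chance that a subject has a fellow-eye-only event is q = 0.80·p_f, and the chance of at least one such subject is 1 − (1 − q)^n.

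| Assumed p_f | Either-eye rate | Bounds without independence | Expected fellow-eye-only subjects, n = 25 | At least one, n = 25 / n = 30 |
|---|---|---|---|---|
| 2% | 21.6% | 20-22% | 0.4 | 33% / 38% |
| 5% | 24.0% | 20-25% | 1.0 | 64% / 71% |
| 10% | 28.0% | 20-30% | 2.0 | 88% / 92% |

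If p_f = 0, nothing changes.

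**The case against.** **The layouts are not visible.** Table layouts belong in Appendix D, which shows only headings in the text available. Titles alone are weak evidence: Table 14.3.3.8 (OCT) has no eye label either, although SAP 13.3.5 covers both eyes. This stands, and it limits the point to the text available. But the case does not rest on titles. SAP 13, SAP 13.2 and Protocol 9.3 name the dimensions of the adverse event summaries, and eye is not one of them.

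**The information is available elsewhere.** SAP section 6 commits to listing individual eCRF data, so laterality, if collected, should appear in Listings 16.2.6.1 to 16.2.6.3, where one fellow-eye event among 25 to 30 subjects is easy to find. Slit lamp, fundus and IOP are also main safety criteria and are tabulated by eye. This is real but partial cover. Listings give no incidence. The examinations carry neither seriousness nor relationship, and SAP 13.3 presents them as catching events that ordinary reporting may miss, so they complement the TEAE tables. They are also intermittent: the schedule has slit lamp and fundus at Day 1 and Day 28 but not Day 7, and OCT only at baseline and Month 12.

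**The relationship effect is thin.** Table 14.3.2.4 pools related and possibly related events. For the fellow eye to change a subject's status, an event in an eye not injected in this study must be counted as related while the study-eye event is not. That can happen, not least because "Adverse events with a missing relationship will be considered related for this summary", but the documents give no basis for calling it common. The table also removes fellow-eye events judged unrelated.

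**A stronger reading to avoid.** A reader might infer that the plan understates the incidence of ocular events after re-injection. It cannot: pooling the eyes can only raise incidence. Nor is the error upward in every cell, as the severity example shows.

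**Conclusion.** The point holds for the text available. As written, SAP 13.2 yields either-eye ocular TEAE figures for a question about one eye. Subject incidence, event counts and cumulative severity equal or exceed the re-injected-eye figures, which is conservative for absolute incidence. Single lower-severity rows of Table 14.3.2.3 can fall below them.

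The only size that needs no assumed rate is the one-subject shift: 0/25 to 1/25, or 0/30 to 1/30, with the upper limits shown above. The other figures rest on assumed rates and independence. The actual overstatement could be zero.

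This is an inexpensive improvement to a descriptive analysis, not a flaw that invalidates it. A reader might also infer that exact intervals or a precision statement should be added. This point does not call for either, because the plan makes no inferential claim on these tables. Confidence is medium, because the Appendix D layouts and the eCRF are not visible.

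**What to change.** In SAP 13.2 and Appendix B:

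1. Keep the all-events TEAE tables. Add three blocks, at minimum for Tables 14.3.2.2 to 14.3.2.5: ocular study eye, ocular non-study eye, and non-ocular.
2. Assign highest severity and closest relationship within each block.
3. Take laterality from data already collected. If the eCRF has no eye field, use site queries or a documented review before lock.
4. Count a bilateral event once in each eye block, and footnote that the blocks do not sum to the total.
5. Show ocular events of unknown eye as a separate footnoted count, and give the study-eye figure with and without them. The figure that includes them fits the SAP's own default for missing dates in Appendix A: "The most conservative approach will be systematically considered".
6. Record the split in SAP section 15. If the database is already locked, label it post hoc, as SAP section 6 requires.

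If the Appendix D layouts already split by eye, it is enough to say so in 13.2.

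**Cost.** SAP text in 13.2 and 15, index entries beyond the minor changes that Appendix B allows without amendment, and extra table blocks. No new assessments are needed. The SAP is dated 09 Nov 2022, after the planned study period ended (Q3 2022), so if laterality was not captured, queries or review will take time and some events may stay of unknown eye.

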13.3 Ophthalmic Safety Assessments

Procedures will be performed at scheduled intervals to specifically assess eye AEs that may not be detected by usual AE reporting and to try and visualize the injected cells.

13.3.1 Slit Lamp and Fundus Exam

The binocular slit lamp examination provides a stereoscopic magnified view of the eye structures in detail, enabling anatomical diagnoses to be made for a variety of eye conditions. Fundus exam allows for inspection of the retina, the cellular graft, and detection of retinal detachment.

13.3.1.1 Slit Lamp

For eye structures of eyelids, eyelashes, conjunctiva, sclera, cornea, and iris, subjects will be tabulated by the categories of Normal, Abnormal not clinically significant (NCS), and Abnormal clinically significant (CS) at each time point, and percentages will be displayed. For anterior chamber flare, subjects will be tabulated by the flare grade and the categories of Abnormal NCS and Abnormal CS.

For syneresis, subjects will be tabulated as Not Obvious and Obvious. For posterior vitreous detachment (PVD), subjects will be tabulated as None, Partial and Complete. For lens status, subjects will be tabulated as Aphakic, Pseudophakic, and Phakic.

For cataract type, subjects will be tabulated as Nuclear, Cortical, Posterior Subcapsular and Other. Subjects will also be tabulated by cataract grades of trace, 1+, 2+, 3+ and 4+.

Slit lamp assessments will be summarized separately for each eye.

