1.0 INTRODUCTION

1.1 Background

1.1.1 Retinitis Pigmentosa

Retinitis pigmentosa (RP) refers to a group of inherited diseases causing retinal degeneration. The cell-rich retina lines the back inside wall of the eye. It is responsible for capturing images from the environment. People with RP experience a gradual decline in their vision because photoreceptor cells (rods and cones) die. Forms of RP and related diseases include Usher syndrome, Leber's congenital amaurosis, rod-cone degeneration, Bardet-Biedl syndrome, and Refsum disease, among others.

In most forms of RP, rods are affected first. Because rods are concentrated in the outer portions of the retina and are triggered by dim light, their degeneration affects peripheral and night vision. When the more centrally located cones - responsible for color and sharp central vision - become involved, the loss is in color perception and central vision. Night blindness is one of the earliest and most frequent symptoms of RP.

RP is typically diagnosed in adolescents and young adults. The classic clinical sign of the disease is the presence of dark deposits in the retina. The main risk factor is a family history of retinitis pigmentosa. It is an uncommon condition affecting about 1 in 4,000 people or roughly 100,000 individuals in the US¹. Cases of RP are associated with a wide variety of known gene mutations, with new mutations still being discovered. The mutations can be inherited from one or both parents or occur spontaneously; the pattern of inheritance can be autosomal recessive, autosomal dominant, X-linked or mitochondrial.

There is no effective treatment for RP; once photoreceptors are lost, they do not regenerate. The rate of deterioration of vision varies from person to person, with most people with RP legally blind by age 40. People with RP also often develop cataracts at an early age or swelling of the retina (retinal edema). Numerous breakthroughs in the treatment of cataract and corneal disease have greatly decreased the incidence of blindness from these causes. In contrast, treatment of retinal and optic nerve disease is more limited, with these conditions now representing major causes of incurable visual loss and a significant unmet medical need.

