7.1.4 Blood Samples for Antibody Testing

Blood samples will be collected for testing for Panel Reactive Antibodies (PRA) and Donor Reactive Antibodies (DRA) from subjects prior to treatment, at 4 weeks post-treatment, and at 6 months post-treatment. Details of preparation/shipping of samples will be provided separately.

7.1.5 **Ophthalmic AEs**

Procedures will be performed at scheduled intervals to specifically assess eye AEs that may not be detected by usual AE reporting and to try and visualize the injected cells. Please refer to the study procedure manual for details of all ophthalmologic assessment procedures.

Slit lamp and fundus exam - The binocular slit-lamp examination provides a stereoscopic magnified view of the eye structures in detail, enabling anatomical diagnoses to be made for a variety of eye conditions. This assessment will include detection of anterior chamber cell or flare; acute cataract development or progression in phakic patients, or vitreous haze. Fundus exam allows for inspection of the retina, the cellular graft, and detection of retinal detachment.

Optos photography - Optos photography includes a widefield dilated Optos photograph of the posterior segment with any cell cluster from the anterior vitreous visualized in the photo frame along with the posterior segment/fundus.

IOP - Intraocular pressure is measured with a tonometer as part of a comprehensive eye examination. Measured values of intraocular pressure are influenced by corneal thickness and rigidity

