13.3.1.2 Dilated Funduscopic Exam

The result from the optic nerve exam, vitreous exam, macula exam and peripheral retina exam will be summarized using counts and percentages of Normal, Abnormal NCS and Abnormal CS and will be presented by eye and time point.

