13.3.4 Clinical Vitreous Exam

For the clinical vitreous exam, counts and percentages will be summarized for method used (Indirect Ophthalmoscopy, Slit Lamp Exam, Other), whether jCell is visualized, the predominant

shape of the jCell (Sphere/Ellipsoid, Strand(s), Diffuse Haze no opacities >2DD, Debris or Graft Remnants and Other), the estimated location of jCell in the vitreous (e.g. anterior 1/3).

Other details collected for the clinical vitreous exam will be provided in a data listing, including date of examination, the secondary shape of the jCell aggregate, size on the horizontal axis, and size on the vertical axis.

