13.3.5 Optical Coherence Tomography (OCT)

OCT results will be summarized in a table showing the counts and percentages of subjects whose eyes (both Study Eye and Non-Study Eye) show cystoid macular edema (CME) present, and of those who show CME, how many cases involve the foveal center; epiretinal membrane formation present and how many have evidence of retinal traction present. In addition, investigator observations of ellipsoid zone (EZ) presence will be summarized as Not Present; Present but Reduced; Present and Near Normal.

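### Slit lamp, cataract, fundus and OCT findings are tabulated as category counts with no shift from baseline, so the tables show net movement but not how many eyes had new or worsened findings

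*SAP*

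**What the plan says.** The primary objective is the safety of repeat injection (Protocol 2.1, SAP 3.1). Protocol 3.2.2 names slit lamp and fundus exam, with IOP, among the main safety criteria. The SAP plans these summaries:

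- **Slit lamp structures (SAP 13.3.1.1):** counts of normal, abnormal not clinically significant (NCS), and "Abnormal clinically significant (CS) at each time point, and percentages will be displayed".
- **Cataract (SAP 13.3.1.1):** "Subjects will also be tabulated by cataract grades of trace, 1+, 2+, 3+ and 4" (top grade 4+), alongside cataract type and lens status. There is no grade for absence of cataract and no stated phakic denominator.
- **Fundus (SAP 13.3.1.2):** "summarized using counts and percentages of Normal, Abnormal NCS and Abnormal CS and will be presented by eye and time point".
- **OCT (SAP 13.3.5):** "counts and percentages of subjects whose eyes (both Study Eye and Non-Study Eye) show cystoid macular edema (CME) present", plus foveal involvement, epiretinal membrane, traction and ellipsoid zone status.

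Neither these sections nor the table titles in Appendix B (14.3.3.1 to 14.3.3.4 and 14.3.3.8) mention a shift, a worst post-baseline value or a count of worsened eyes. By contrast, change from baseline is planned for IOP (13.3.3), laboratory values (13.4) and vital signs (13.5).

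The SAP defines baseline for efficacy variables (10.2), laboratory values and vital signs, but not for these exams. Protocol Table 2 schedules slit lamp and fundus exams at both Screening and Baseline.

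Protocol 7.1.5 says the slit lamp exam should pick up "acute cataract development or progression in phakic patients". Protocol 1.1.1 says "People with RP also often develop cataracts at an early age or swelling of the retina (retinal edema", and gives dark retinal deposits as the classic sign of the disease.

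**The concern.** Development or progression of cataract is a change within an eye, and so is a new macular or retinal finding after re-injection. A count at each visit is a margin: it equals the baseline count plus eyes that became abnormal, minus eyes that ceased to be, with any change in who was examined mixed in. SAP 6 takes percentages over non-missing observations, so the denominator can move between visits too.

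If no eye starts in an abnormal category, this matters little. If some do, worsening in one eye can be offset by improvement or a missed visit in another. Protocol 1.1.1 gives reason to expect some such eyes for lens, macula and retina. A reader of the safety tables would then not know how many re-injected eyes got worse, which is the number wanted from a main safety criterion.

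**Working it through.** The plan gives no figure to reproduce: the 25 to 30 subjects are set by availability (SAP 5), with no event rate. The check is therefore what two sets of counts can and cannot reveal. All counts below are assumptions for illustration; only the sample size range is from the documents.

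**Two categories (normal, abnormal).** Let n be eyes examined at both visits, b abnormal at baseline and f abnormal at follow-up. The number of newly abnormal eyes must lie between max(0, f − b) and min(f, n − b). With n = 25:

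| b | f | Lower bound | Upper bound |
|---|---|---|---|
| 10 | 10 | max(0, 0) = 0 | min(10, 15) = 10 |
| 10 | 12 | max(0, 2) = 2 | min(12, 15) = 12 |
| 0 | 3 | max(0, 3) = 3 | min(3, 25) = 3 |

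With n = 30 the three ranges are the same. The last row shows that the counts are exact when no eye is abnormal at baseline.

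**Fundus, three categories (normal/NCS/CS), n = 25.**
- 0/20/5 at both visits: 0 to 5 eyes may have worsened.
- 0/20/5 then 0/17/8: at least 8 − 5 = 3 worsened, and up to 8 (if all 5 CS eyes improved and 8 others replaced them).

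**Cataract grade (none/trace/1+/2+/3+/4+), n = 25.** The minimum and maximum number of worsened eyes consistent with both margins were found by linear programming.
- 10/6/6/3/0/0 at both visits: 0 to 15 worsened if grades may move either way; 0 if no eye can improve.
- 10/6/6/3/0/0 then 8/6/6/4/1/0: 2 to 17 worsened if grades may move either way; 2 to 7 if no eye can improve.

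Even under the natural assumption that cataract does not regress, the counts in the last example leave the number of progressing eyes uncertain by a factor of more than three.

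**What a shift table would do.** It cross-classifies each eye's baseline category against its later category, so each of these ranges becomes one number. It has one limit. If all 25 eyes are CS at both visits, the shift table shows no movement even if a new lesion has appeared. That case needs tabulation by specific finding.

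**The case against.** The strongest reply is that the information is not lost.

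- **Listings.** SAP 6 and Appendix B (16.2.7.x) list slit lamp, fundus and OCT results by subject. With 25 to 30 subjects, each course can be read by hand. This stands, but a listing does not summarize, and the reader would have to derive the result of a main safety criterion personally.
- **TEAE tables.** Protocol 8.1 counts new conditions and worsening of pre-existing ones as AEs, and SAP 13.2 tabulates them. This also stands in part. However, SAP 13.3 says the exams are there to find eye events that ordinary AE reporting may miss. Protocol 8.1 also excludes expected progression of RP, so whether a lens or macular change is reported depends on the investigator's judgment.
- **Lens status.** A reader might infer that an eye leaving the cataract grades through surgery disappears from view. It does not: the lens-status row would show it as pseudophakic, and procedures are listed (SAP 14.1).

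A reader might also infer that most eyes start abnormal. The documents give no proportion, and Protocol 4.2 excludes clinically significant macular edema and subjects expected to need cataract surgery within a year. Nor do they suggest that RP makes eyelids, conjunctiva, cornea or iris abnormal; the argument is for lens, macula and retina.

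It is tempting to extend the point to the visibility of injected cells, since every study eye was injected before. SAP 13.3.4 has a separate shape category for debris or graft remnants, so the documents do not support treating that as the same fault.

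**Conclusion.** The point holds in a limited form. The planned tables reveal net movement between visits, including net worsening. They do not give the number of eyes with new or worsened lens, macular or retinal findings. A reader might infer that worsening would be invisible; the counts by grade, the lens-status row, the listings and the TEAE tables show that it would not be.

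The size of the gap depends on how many eyes are abnormal at entry, which the documents do not state. In the illustration, 10 of 25 abnormal at both visits leaves 0 to 10 newly abnormal eyes possible; with none abnormal at baseline the gap closes.

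Two things cannot be checked: the table shells in SAP Appendix D have no visible content, so a shift layout there cannot be ruled out, and the eCRF is not available. The SAP text and table index give no sign of such a layout. This is an inexpensive improvement to the primary safety reporting, not a flaw that invalidates it.

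**What to change.** In SAP 13.3.1, 13.3.5 and Appendix B:

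1. Define baseline for the eye exams as the last value before injection.
2. Add tables, with study and non-study eye side by side, of the shift from baseline to the worst post-injection category for cataract grade, each fundus structure, CME, epiretinal membrane and traction. For OCT, which Protocol Table 2 schedules only at Baseline and at Month 12 or early termination, use the shift between those two.
3. For cataract, add a 'none' grade, use eyes phakic at baseline as the denominator, and count a grade increase or cataract surgery as progression.
4. Where a fundus structure is already abnormal at baseline, tabulate new or worsened findings by specific finding from the recorded data, because a shift between categories cannot show a change within one.

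The shift tables use assessments already scheduled and need no change in conduct. Step 4 depends on how the eCRF records findings. The cost is a few more tables, with small cells at 25 to 30 subjects. The change belongs in the SAP before database lock, because SAP 6 labels anything added later as post hoc.
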